## **2.4 Control group**

The treatment received by young people in the control group consists of 'service as usual' i.e., the typical provision provided by the DPO or by an agency to which they refer a young person, including group sessions, sports, and trips, but excluding one-to-one support. The intervention group would similarly be expected to receive services as usual as well as mentoring.

---

 McNeil & Stuart (2022) <https://www.youthimpact.uk/key-resources/outcomes-framework-21>

## 3 Impact evaluation

### 3.1 Research questions or study objectives – impact evaluation

The primary question addressed by the efficacy trial will be: What is the impact of short-term mentoring on the social and emotional learning skills of young people at risk of youth violence, compared with services as usual?

The Strengths and Difficulties Questionnaire (SDQ) will provide the primary social and emotional learning outcome measure. Secondary social and emotional learning outcomes will be belief-based measures focusing on: (a) self-confidence (leadership and communication); (b) problem-solving and decision-making skills; (c) teamwork and social skills building; (d) resilience/emotional regulation. For full details of the outcome measures see section 4.

### 3.2 Design – impact evaluation

The efficacy trial will be run as a RCT within an expected 17 DPOs. The trial will have two arms per DPO: an intervention arm, and a wait-list control arm. Randomisation will occur on an individual basis and allocation will be in the ratio 50:50 per DPO. Table 2. provides a full summary of the trial design.

DPOs will be responsible for recruiting young people to the trial, with the target for each DPO being 50 young people. For those recruited and deemed eligible (see section 3.4), consent will be collected from both parent/carer and young person, and the young person will complete an online baseline questionnaire including the primary and secondary outcome measures prior to randomisation. The DPOs will complete basic demographic details (including age, ethnicity, gender and whether this is the same as sex assigned at birth) about the young person. Once the consent has been collected and the baseline questionnaire completed, the young person can enter the trial, with random allocation taking place at that point.

Those randomised to the intervention arm will start mentoring as soon after randomisation as is feasible; those allocated to the control arm will be eligible to start mentoring after 12 weeks, once they have completed their follow-up outcomes survey.

Data on outcomes will be collected at two points in time per young person: baseline and at, or soon after, 12 weeks post randomisation. Supporting data will be collected throughout the trial, described more fully below, and covering:

- demographics (baseline)
- number of sessions of mentoring (intervention arm only)
- receipt of other services during the trial (both arms)

- whether any control group member started mentoring before the 12-week outcome survey was completed

An online 'data portal' has been developed to capture all of the quantitative trial data. This includes an embedded randomisation tool.

**Table 2. Trial design**

Trial design, including number of arms		Two-arm randomised waitlist controlled trial
Unit of randomisation		Individual young person
Stratification variables (if applicable)		DPO
Primary outcome	variable	Social and emotional learning skills
	measure (instrument, scale, source)	Strengths and Difficulties Questionnaire, young people self-report (Goodman et al, 1998), fielded in online survey 12 weeks after randomisation.
Secondary outcome(s)	variable(s)	Self-confidence; problem-solving/decision-making; teamwork/social skills building; emotional regulation/resilience
	measure(s) (instrument, scale, source)	Self-report items from the Evaluation of the National Citizen Service (Fitzpatrick et al, 2021), fielded in online survey 12 weeks after randomisation
Baseline for primary outcome	variable	Social and emotional learning skills
	measure (instrument, scale, source)	Strengths and Difficulties Questionnaire, young people self-report (Goodman et al, 1998), fielded in online survey prior to randomisation
Baseline for secondary outcome	variable	Self-confidence; problem-solving/decision-making; teamwork/social skills building; emotional regulation/resilience

	measure (instrument, scale, source)	Self-report items from the Evaluation of the National Citizen Service (Fitzpatrick et al, 2021), fielded in online survey prior to randomisation
--	-------------------------------------	--

### 3.3 Randomisation

Randomisation will be built into the online data portal. Prior to the start of the trial a ‘randomisation’ column per DPO will be generated in Excel by the trial statistician. The columns will be added to the portal but hidden from all but a few members of the evaluation team. A copy of the Excel sheet will be archived before the start of the trial so that it is possible to check for any divergence from the randomisation once the trial has started.

The randomisation algorithm is to be based on a merged block randomisation procedure which is appropriate for multi-site trials. It allows for randomisation to be undertaken over time, rather than in batches, but ensures good balance between the two arms both overall and over time.

From the perspective of DPOs, the randomisation button on the data portal will only be enabled once consent has been recorded as collected and the young person baseline questionnaire completed. Once ‘clicked on’ the randomisation is completed, and the allocation recorded. There is no possibility of it being changed or re-run and DPOs cannot influence the allocation.

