## 10 Timeline

Table 6. below sets out the intended timetable. We anticipate that most DPOs will want to recruit young people in a rolling process, either individually or in small groups, with those randomised to the intervention group starting mentoring once entered into the trial, and their controls starting 12 weeks later. The 12-week delivery timeline may be slightly adjusted in individual DPOs to support those whose delivery is markedly affected by school summer holidays. We will work closely with the DPOs to establish their capacity constraints and how best to recruit young people to the trial and ensure that delivery takes place within the intended window. The recruitment period for the feasibility trial was extended as DPOs needed longer for recruitment than expected, and we have taken this into account in the timeline for the efficacy trial. We have allowed 11 months overall for recruitment and completion of mentoring for the intervention group (25 young people per DPO).

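### The protocol says DPOs cannot influence the allocation, but nothing fixes who takes the next slot when several young people are ready, so influence through order or timing of entry is not excluded

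*Protocol*

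**What the plan says.** Protocol section 3.3: "Prior to the start of the trial a ‘randomisation’ column per DPO will be generated in Excel by the trial statistician". The method is "based on a merged block randomisation procedure", which, the protocol says, "ensures good balance between the two arms both overall and over time". The columns sit in the portal but are "hidden from all but a few members of the evaluation team", and an archived copy allows later checks for departures from the list. The DPO's button opens once consent is recorded and the baseline questionnaire is complete, and one click records the result. The section concludes: "There is no possibility of it being changed or re-run and DPOs cannot influence the allocation".

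Section 3.2 adds that "allocation will be in the ratio 50:50 per DPO" and that allocation happens when consent and baseline are complete. Section 10 expects that "most DPOs will want to recruit young people in a rolling process, either individually or in small groups". Appendix 2 encourages joint onboarding sessions that collect documents for several young people together, and shortlisting before the start date. Under section 3.4, DPO staff judge the level of need and set the threshold for the cases they put forward.

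**The concern.** Two kinds of protection need to be kept apart. One is protection of the slot: staff cannot see the next entry, change it or draw again. Section 3.3 provides this. The other is protection of the match between slot and person: staff cannot decide who receives the next entry once they can partly predict it. Section 3.3 claims this too, but the procedure it describes does not secure it.

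A list kept balanced over time within a DPO is partly predictable from its own past. Staff knowledge of that past is not stated, but it follows from the open wait-list design, because the DPO starts or delays the mentoring itself. If two or three young people are ready together, the order of clicks decides who meets the more likely arm.

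The archived list would not reveal this, since reordering people leaves the column intact. Organisation fixed effects (section 4.6) do not remove it, because it arises within a DPO. Adjustment for baseline outcomes removes only what those scores capture. At stake is a between-arm difference in traits that staff can see, such as need or motivation, and the reader's reliance on the sentence when judging selection bias.

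**Working it through.** The protocol gives no figure on this point, so there is none to reproduce. The check asks how predictable the next slot is, and what a between-arm gap could amount to.

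**Inputs from the protocol.** 50 young people per DPO, 1:1 within DPO, merged blocks (sections 3.2 and 3.3); MDES 0.17 SD (Table 3), used only as a yardstick.

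**Assumptions not in the protocol.** Two independent permuted-block lists merged by a fair coin; block lengths 2 to 8; staff guess the arm with fewer allocations so far and toss a coin when level; need distributed as N(0,1); three young people ready; a residual effect of need on the outcome of 0.2 to 0.3 SD per SD after baseline adjustment. That the protocol leaves block length unstated is no fault, since it should stay unknown to DPOs.

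**Step 1: predictability** (simulated lists of 50).

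| Block length | Merged blocks, correct guesses | Ordinary permuted blocks |
|---|---|---|
| 2 | 69% | 75% |
| 4 | 65% | 70% |
| 6 | 62% | 68% |
| 8 | 61% | 66% |

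Simple randomisation gives 50%.

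Block length 2 can be checked by hand. In the long run, a quarter of the time both lists are at the start of a block, and the guess is right with probability 0.5. Half the time exactly one list is mid-block, and it is right with probability 0.5 × 1 + 0.5 × 0.5 = 0.75. A quarter of the time both are mid-block, again 0.5 × 1 + 0.5 × 0.5 = 0.75. The total is 0.25 × 0.5 + 0.5 × 0.75 + 0.25 × 0.75 = 0.69, as simulated.

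**Step 2: gap in need between the arms, block length 4, three ready.** The result turns on how the ready group behaves.

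- *Batch cleared before the next arrives:* about 0.10 SD if staff steer at every click and 0.06 SD if they steer at half. Other runs gave as little as 0.07 and 0.04 SD.
- *Pool topped up to three before every click:* about 0.25 SD with full steering and 0.13 SD with half. This lets staff hold a ready person back indefinitely.
- *Fixed queue:* 0.00 SD.

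Block length matters as well. With the topped-up pool and full steering the gap runs from 0.12 SD (block 8) to 0.42 SD (block 2). With cleared batches and full steering it is about 0.04 SD at block 8.

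**Step 3: bias on the outcome at block 4** = gap × residual effect.

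- Batches, low end: 0.06 × 0.2 = 0.012 SD; 0.012 / 0.17 = 7% of the MDES.
- Batches, high end: 0.10 × 0.3 = 0.03 SD; 0.03 / 0.17 = 18%.
- Standing pool, full steering: 0.25 × 0.3 = 0.075 SD, about 0.08; 0.075 / 0.17 = 44%.

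If nobody steers, the bias is zero at every block length.

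**The case against.** The strongest reply is that the sentence is true in its natural sense: the list is concealed, and a result can be neither altered nor redrawn. That stands, and it is why the sentence is overstated rather than simply wrong.

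Second, section 3.2 places allocation at the point of completion, which leaves little choice if followed. Consent by email or paper and surveys on personal devices (sections 3.4 and 4.4) would also stagger readiness. This stands as a statement of intent, but section 3.3 implements it as a manual click with no order or time limit, and joint onboarding works the other way.

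Third, there are safeguards. Table 4 lists demographics as regression covariates and plans a descriptive comparison of the arms; section 4.4 shows that these data include care status, free school meals, special needs and referral route. Young people in crisis, or for whom waiting could be harmful, are excluded (section 3.4), and controls may start mentoring after 12 weeks, so the motive to steer is weaker. Merged blocks are less predictable than ordinary blocks of the same length. All of this reduces the risk, but none of it fixes the order.

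Fourth, the Delivery Handbook and portal manual (section 2.2) are not at hand and may contain an order rule. If so, section 3.3 need only state it.

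A reader might go further and infer that staff do pick whom to click, that the arms are therefore biased, or that the bias is a large share of the MDES. The protocol supports none of these. It does not describe a waiting pool or say who presses the button, and the larger figures need a standing pool with steering at every click.

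**Conclusion.** The point holds as a gap between an absolute claim and the procedure that is meant to deliver it. DPOs cannot see or change an allocation, but they control the order and timing of entry on a balanced list whose past they probably know. Influence is possible; the protocol does not show that it occurs.

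Predictability of about 61% to 69% rests on the assumed merged-block construction and block lengths of 2 to 8. The size of any bias rests further on pool size, steering rate and residual effect, none of which the protocol gives. Of the two patterns in the working, clearing each batch before the next is closer to what sections 3.2 and 10 describe, so the lower figures are the fairer guide. The topped-up pool at block 4 is an upper case for that block length, not an expectation. This is a cheap improvement worth making, not a defect that undermines the trial.

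**What to change.** If recruitment is still open, have the portal decide the order. When a DPO presses the button, the next column entry goes to the ready young person at that DPO with the earliest time stamp for completed consent and baseline. A ready person is passed over only through a withdrawal logged before allocation. Replace the absolute sentence in section 3.3 with this rule.

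The cost is a small portal change and a sentence of text, with no extra participants. The downside is that DPOs can no longer randomise a particular ready person first, for instance to suit one mentor's availability. They can still choose when to press.

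The portal change may come too late. Table 6 plans a hard stop to recruitment in August 2023, and the current version is dated 09/10/2023. If recruitment has closed, and for anyone already randomised, two steps remain. Restate the sentence to say only that DPOs cannot see or change an allocation. Where the portal holds the time stamps, which the protocol does not confirm, report how often click order departed from readiness order.

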### 3.4 Participants

#### *DPO characteristics*

The 17 DPOs are located in:

- Greater London – 3
- South East – 2
- Yorkshire – 4
- East Midlands – 1
- East Anglia – 2
- South West – 1
- West Midlands – 2
- South Wales – 1
- Pan-Wales – 1

---

 Merged block randomisation: A novel randomisation procedure for small clinical trials. Stephanie L van der Pas. Clinical Trials (2019) Vol 16(3) 246-252

The DPOs represent a range of youth work provision and work with a variety of populations. For some DPOs, mentoring is their primary or only offer, for others it is their highest level of support available, while in others it is the lowest level of support available. DPOs also represent a mix of rural and urban populations. Most DPOs deliver mentoring from a central location or youth centre, while some deliver within schools or detached mentoring.

### *Young people*

The eligibility criteria for recruitment of young people to the efficacy trial will be identical to those for the feasibility trial. DPOs will identify and approach young people for the trial who:

- are aged between 10 and 14 (or up to 17 by exception, with no more than 30% of young people aged 15 to 17 per DPO) and
- exhibit at least one of the YEF-listed risk factors for youth violence (shown in Appendix 4.) and
- DPO staff deem at a suitable level of need for 12-weeks of mentoring. The only exclusion criterion is that DPOs must exclude young people facing immediate risk or crisis, or for whom being on a waiting list would be potentially harmful. DPOs are responsible for determining the threshold of cases that they put forward for the trial.
- DPOs can use a range of referral routes (school, YOT, CAMHS, other health, social care, existing service user, self-referral, friends or family referral or other) to identify potentially eligible young people.

The intervention (mentoring) will take place on site at DPOs, in schools, or other appropriate site in line with DPOs usual delivery, and a minority of sessions may be delivered online as appropriate. The feasibility trial showed that online sessions are employed rarely so we will not enforce a limit, but the format of sessions will be recorded as part of the administrative data.

In order to take part in the trial, both young people and their parent/carers will be required to provide written consent. The process involved is:

- The DPO introduces the young person to the idea of mentoring and participation in the trial
- Young people are given a child-friendly information sheet explaining what their participation involves, and provided with opportunities to ask questions

---

 The shared practice model does not specify a limit to this, given the varying reasons for online sessions.

- Eligible young people are asked to sign a consent form which sets out the data that will be collected, how it will be used, plans for archiving, and seeks consent for participation in the trial and the qualitative interviews
- Parent/carer consent is also sought, DPO staff will explain participation in the trials to each young person's parent/carer then send them a consent form and information sheet by email or give them paper copies. This form also seeks consent to the young person taking part in a qualitative interview if the young person agrees to this when approached at the end of their mentoring
- DPOs will be encouraged to hold sessions for young people and parent/carers together to explain mentoring and participation in the trial, respond to queries and concerns, and collect consent

### 3.5 Sample size calculations

As shown in Table 3., each DPO will have a target of recruiting and randomising 50 young people and delivering mentoring to them, with 50 being set as a challenging, but achievable, number. The expectation is that, across all the DPOs, this will give a trial of around 850 young people, around 425 per arm. Assuming that follow-up data collection is achieved with around 90% this will give an analysis dataset with around 382 per arm. (Follow-up data collection was achieved for 85% of young people taking part in the feasibility trial, but for an efficacy trial we will aim to increase this to at least 90%.)

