**Table 3. Sample size calculations**

		PARAMETER
Minimum Detectable Effect Size (MDES)		0.17sd
Pre-test/ post-test correlations	level 1 (participant)	0.5
	level 2 (cluster)	0
Intracluster correlations (ICCs)	level 1 (participant)	0
	level 2 (cluster)	0

		PARAMETER
Alpha 		0.05
Power		0.8
One-sided or two-sided?		Two
Number of participants	Intervention	425
	Control	425
	Total	850

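### Table 3's MDES of 0.17 SD fits the 425 per arm randomised; the roughly 382 per arm that section 3.5 expects to analyse gives 0.18 SD

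*Protocol*

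**What the plan says.** Section 3.5 of the protocol sets 50 young people per organisation as the target and concludes that "this will give a trial of around 850 young people, around 425 per arm". It then allows for loss to follow-up: "Assuming that follow-up data collection is achieved with around 90% this will give an analysis dataset with around 382 per arm". It is open about the basis for that rate, reporting that "Follow-up data collection was achieved for 85% of young people taking part in the feasibility trial" and that the efficacy trial aims for at least 90%. Table 4 repeats the 90% as a minimum of 765 completed follow-ups in total.

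Table 3 gives the result of the calculation: "Minimum Detectable Effect Size (MDES) 0.17sd". Its inputs are a participant-level pre/post correlation of 0.5, ICCs of 0, alpha 0.05 and power 0.8, and on sidedness it states "One-sided or two-sided? Two". The only participant numbers in the table are 425, 425 and 850. The protocol does not say which sample size the MDES rests on, and it gives no separate MDES for 382 per arm.

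**The concern.** An MDES describes the comparison that will actually be made, so it should rest on the number expected in the analysis. The text above Table 3 names that number, and the table shows a different one beside the MDES. If 0.17 SD was worked out from everyone randomised, the 10% loss just stated never reached the headline figure, and the design as described has less than 80% power at 0.17 SD.

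What is at stake is the accuracy of the only sensitivity figure the protocol gives. It would look slightly better than the plan supports, and more so if follow-up falls back to the rate seen in the feasibility trial.

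**Working it through.** **Inputs**
- Correlation r = 0.5, ICC 0, two-sided alpha 0.05, power 0.80: Table 3.
- Allocation 1:1: section 3.2, "allocation will be in the ratio 50:50 per DPO".
- Regression adjusted for the baseline outcome: section 4.6. The residual variance factor is therefore 1 − 0.5² = 0.75.
- n per arm: 425 randomised and 382 analysed at 90% (section 3.5); 361 if the feasibility rate recurs (0.85 × 425 = 361.25).

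**Formula**

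MDES = (z₀.₉₇₅ + z₀.₈₀) × √[(1 − r²) × 2/n] = (1.960 + 0.842) × √(1.5/n)

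Power at 0.17 SD = Φ(0.17/√(1.5/n) − 1.960)

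**Step 1: reproduce the stated figure.** With n = 425, √(1.5/425) = 0.0594 and 2.802 × 0.0594 = 0.166, which rounds to 0.17. Power at 0.17 SD is 81.6%.

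**Step 2: put in the plan's analysed number, then the feasibility rate.**

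| n per arm | Basis | MDES (SD) | Power at 0.17 SD |
|---|---|---|---|
| 425 | all randomised | 0.166 | 81.6% |
| 382 | 90% follow-up | 0.176 | 77.4% |
| 361 | 85% follow-up | 0.181 | 75.1% |

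**Step 3: number needed for exactly 0.17 SD at 80% power.** n = 1.5 × (2.802/0.17)² = 407.4, so 408 analysed per arm, and 408/425 = 96% follow-up. The lowest n that still prints as 0.17 is 385 per arm (0.1749), and 385/425 = 90.6% follow-up.

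**Step 4: could another method give 0.17 at 382?**

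| Method | MDES at 425 | MDES at 382 |
|---|---|---|
| t-based, fixed effects for 17 organisations | 0.167 | 0.176 |
| No covariate, or change score | 0.192 | 0.203 |
| r² = 0.5 | 0.136 | 0.143 |
| One-sided | 0.148 | 0.156 |

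None gives 0.17 at 382 per arm. Table 3's inputs with 425 per arm do.

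**The case against.** The gap is within the precision of the inputs. Section 3.5 hedges its counts and its follow-up rate as approximate, and the correlation is given to one decimal. At 382 per arm, r = 0.45 gives 0.181, r = 0.505 gives 0.17497 (which prints as 0.17) and r = 0.55 gives 0.169. The value 0.1756 lies just over a rounding boundary, and three more young people per arm would bring it back under. The 90% is also a minimum target. All of this stands, and it limits the importance of the point. It does not reconcile the figures, because the protocol fixes r at 0.5 and names 382 as the number analysed.

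The cause is also inferred. Use of the randomised number is the likeliest explanation, but the protocol does not say so, and 0.1756 truncated would also read 0.17. Nor is attrition concealed: the 90% assumption, the 382 and the feasibility trial's 85% all stand in the text.

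Three stronger readings are tempting, and the documents do not support them:
- A reader might infer that 0.17 SD requires every randomised young person to be analysed. It does not: about 408 per arm is enough, and from 385 the figure still rounds to 0.17.
- A reader might infer that the trial is too small and should recruit more; 454 randomised per arm at 90% follow-up would give 0.17 SD. The protocol sets its size by what the organisations can recruit and reports the MDES that follows, and it nowhere calls 0.17 SD a required effect. The current version is also dated October 2023, after the scheduled August 2023 end of recruitment.
- A reader might infer that a null result would be misjudged against 0.17 rather than 0.18. The protocol does not say that the MDES will be used in that way, and section 4.1 already warns that a significant effect on the SDQ at 12 weeks is highly unlikely. A null result should be read from its observed confidence interval, not from a planning value.

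**Conclusion.** The point holds as a minor inconsistency. On Table 3's own inputs, 0.17 SD at 80% power matches the number randomised and not the number section 3.5 says will be analysed. At 382 per arm the MDES is 0.176 SD, and power at 0.17 SD falls 2.6 points short of the stated 80%. At 85% follow-up the shortfall is about 5 points (80 − 75.1).

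This rests on the baseline-adjusted normal-approximation formula, r = 0.5, no clustering and equal arms. It also assumes that every completed follow-up yields a usable SDQ score. Section 4.4 lets young people skip questions, so the usable number could be somewhat lower, but the protocol gives no figure for this and none is assumed here. The design and the analysis are unaffected.

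**What to change.** In Table 3, restate the MDES as 0.18 SD for about 382 analysed per arm (90% follow-up), and note that it is also 0.18 SD (0.181) at 85% follow-up. Show the analysed numbers beside the randomised ones. If 0.17 SD is kept, label it as the value with no attrition. Do not carry 0.18 SD forward as a benchmark for interpreting a null result.

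The cost is a line or two of wording in one table and a slightly less favourable headline figure. Recruitment, follow-up targets and analysis stay as they are.
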